2.4.8 Analyses of Anti-Drug Antibody (ADA)

The percentage of subjects developing ADA will be summarized by cohort. A listing will be provided for ADA data.

2.4.9 Analyses of Immunoglobulins

The descriptive summary and change from baseline of Immunoglobulins will be summarized by cohort. A listing will be provided for Immunoglobulins data.

2.5 Data Handling Conventions

Data handling discussions for the primary efficacy is included in Section 1.2.1. The further discussion for the data handling conventions for other variables will be included in this section.

General conventions

The following formulas will be used for computations of parameters.

Demographic formulas:

The age variable recorded in the eCRF will be used for analysis, no derived age variable is planned as only the year of birth is reported.

$$\text{BMI (in kg/m}^2\text{)} = \frac{\text{weight in kg}}{\text{height (in cm)} \times \text{height (in cm)}} \times 10000$$

Renal function formulas:

Creatinine clearance value will be derived using the equation of Cockroft and Gault. The calculation requires body weight and age. The last weight measurement on or before the visit of the creatinine measurement will be used. If available, the age used by central lab at the visit will also be used for this derivation, otherwise the age at informed consent will be used. Additionally, eGFR based on MDRD will be calculated.

$$crcl \text{ (mL/min)} = \frac{(140 - \text{age}) \times \text{weight(kg)}}{0.814 \times \text{creatinine(umol/L)}} \text{ (For males)}$$

$$crcl \text{ (mL/min)} = \frac{(140 - \text{age}) \times \text{weight(kg)}}{0.814 \times \text{creatinine(umol/L)}} \times 0.85 \text{ (For females)}$$

2.5.1 Missing Data

For categorical variables, subjects with missing data are not included in calculations of percentages unless otherwise specified. The number of subjects with missing data will be presented.

For data listings, the character date will always be used to present the date collected in the eCRF, which allows the actual recorded date to be shown if elements are unknown/missing.

[2.5.1.1 Multiple sclerosis medical history variables](#)

If the date of first MS diagnosis, first symptoms of MS, most recent relapse onset or start and end of previous MS treatments are incomplete, (i.e., month is unknown or day is unknown), unknown month/day will be set to July 1st, an unknown day will be set to the 15th.

[2.5.1.2 Adverse event information](#)

Adverse event start date

AE start date will be used for AE classification and analysis. If AE start date is not complete, then the character variable will keep the original incomplete date, the numerical date variable will be imputed and an imputation flag will indicate which date component is missing.

If AE start day is missing, and AE start month and year are not missing:

If AE start year is the same as first dose year and the AE start month is the same as the first dose month) then impute AE start day using the day of first dose. If this leads to a date after the AE end date, use AE end date instead. Otherwise (AE start year is not the same as first dose year and/or AE start month is not the same as the first dose month) impute the AE start day using the first day of the month. If this leads to a date before informed consent, the informed consent date will be used. Imputation flag is 'D'.

If AE start month is missing, and AE start year is not missing:

If AE start year is less than the first dose year, use the informed consent day and month. If AE start year is equal to the first dose year, use the first dose day and month. If this leads to a date after the AE end date, use AE end date instead. If AE start year is after the first dose year, use 1 January. Imputation flag is 'M'.

If AE start year is missing:

Impute AE start date using the day of first dose. If this leads to a date after the AE end date, use AE end date instead. Imputation flag is 'Y'.

Adverse event end date

The general recommendation is not to impute AE end date. However, since AE end date will be used for AE starting date imputation, In order to carry through the logic for programming, the following intermediate step will be used. Afterwards, the original character/numeric date recorded in CRF and supportive imputed end date will be kept in the final analysis dataset.

If AE end day is missing, and AE end month and year are not missing:

Impute AE end date using the last day of the month. If this leads to a date after end of follow-up date, use end of follow-up date instead.

If AE end month is missing, and AE end year is not missing:

Impute AE end date using 31 December as the day and month. If this leads to a date after end of follow-up date, use the end of follow-up date instead.

If AE end year is missing:

Impute AE end date using the end of follow-up date.

Severity of adverse event

If the severity is missing for one of the treatment emergent occurrences of an AE (the same SOC/PT), the maximal severity on the remaining occurrences will be considered. If the severity is missing for all the occurrences a “missing” category will be added in summary table.

Relationship to investigational product

If the assessment of the relationship to investigational product is missing, then the relationship to investigational product has to be assumed as related and the AE considered as such in the derived analysis variable.

Adverse event Listings

For date variables, only character date variables will be presented, and no imputed dates will be printed in the listings. If the AE start date is imputed, then the onset relative day will be empty; if the AE start date or end date is imputed, then AE duration will be empty.

[2.5.1.3 Prior and concomitant medication date](#)

Medication start and end date will be used for prior, concomitant and follow up medication classification and potential analysis for specific medications. To keep the data integrity, if the date is not complete, then the character variable will keep the original incomplete date, the numerical date variable will be imputed (impute the end date first) and an imputation flag will indicate which date component is missing. Only the character variable will be used in data listing.

As prior and concomitant medications are flagged using the recorded start and end dates, it is not possible to apply different imputation rules based on the prior/concomitant status of a record. So the same algorithm will be used for all records made in the “prior/concomitant medication” section of the eCRF.

Prior/Concomitant medication start date

If start day is missing, and start month and year are not missing: Impute the start day using the first day of the month. Imputation flag is ‘D’.

If start month is missing, and start year is not missing: Impute the start day using 1 January. Imputation flag is ‘M’.

If start year is missing: No imputation will be done.

Prior/Concomitant medication end date

If end day is missing, and end month and year are not missing:

Impute end date using the last day of the month. If this leads to a date after end of study date, use end of study date instead. Imputation flag is 'D'.

If end month is missing, and end year is not missing:

Impute end date using 31 December as the day and month. If this leads to a date after end of study date, use the end of study date instead. Imputation flag is 'M'.

If end year is missing:

Impute date using the end of study date. Imputation flag is 'Y'.

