### 10.5 ADVERSE EVENTS (AE'S) AND TREATMENT EMERGENT ADVERSE EVENTS (TEAE'S)

---

All AEs and SAEs occurring on study will be listed by patient. The frequency and percentages of subjects with treatment-emergent adverse events (TEAEs) will be tabulated by system organ class (SOC) and PT, where treatment-emergent is defined as any AE that:

- Occurs after first dosing of study medication and through the end of the study or up through 30 days after the last dose of study treatment, or

- Is considered treatment-related regardless of the start date of the event, or
- Is present before first dosing of study medication but worsens in intensity or the investigator subsequently considers treatment-related.

TEAEs that are considered at least possibly related to study treatment will be tabulated as well as deaths, SAEs, and events resulting in treatment discontinuation.

AEs that occur after informed consent but before first dosing of study medication will not be summarized but will be listed.

At each level of summarization, a patient will be counted only once for each AE, SOC, or PT experienced within that level. In the summation for AE severity, within each level of AE, SOC, or PT experienced, the one with the highest severity will be included. In the summation for AE's relationship to the study drug, within each level of AE, SOC, or PT experienced, the one with the closest relationship to the study drug will be included.

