## 10.7 ADVERSE EVENTS / SERIOUS ADVERSE EVENT CAUSALITY ASSESSMENT

---

The Investigator must also assess the relationship of any adverse event to the use of study drug, (whether none, one, or all) based on available information, using the following guidelines:

1. **Not Related:** Clear-cut temporal and/or mechanistic relation to a cause other than the study drug.
2. **Doubtful:** There is no reasonable possibility that the event is related to the study drug but a definite cause cannot be ascertained.
3. **Possible:** There is still a reasonable possibility that the cause of the event was the study drug but there exists a more likely cause of the event such as complications of progressive disease.

4. **Probable:** The most likely cause of the event is the study drug but other causes cannot be completely excluded.
5. **Definite:** Clear cut temporal and/or mechanistic relation to the study drug. All other causes have been eliminated. Events classified as definite will often be confirmed by documenting resolution on discontinuation of the study drug and recurrence upon resumption.

In the summary of drug related AEs, Categories 1 and 2 will be considered as “Not Drug Related” and all other categories, including missing, will be considered as “Drug Related.”

---

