2.1.4.1 Adverse Events

Adverse events will be coded and classified according to the System Organ Class (SOC) and Preferred Term (PT) using the Medical Dictionary for Regulatory Activities (MedDRA).

The occurrence of AEs (including SAEs and adverse events of special interest [AESIs]) will be captured from the time the informed consent is obtained until the participant terminates participation in the study.

AESI will be categorized using a grouped set of MedDRA terms based on Standardized MedDRA Queries (SMQs) and clinical concept, as determined by the Sponsor. The MedDRA terms selected for AESI analysis will be provided in the Clinical Study Report (CSR).

Suicidal ideation and behavior will be identified by the AE preferred terms included in MedDRA SMQ “Suicide/self-injury”.

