2.4.5.1 Analysis of Adverse Events

The Treatment-Emergent Adverse Events (TEAE) is defined as any AE that:

- Occurs after first dosing of study medication and through the end of the study or up through 30 days after the last dose of study treatment, or
- Is considered treatment-related regardless of the start date of the event, or
- Is present before first dosing of study medication but worsens in intensity or the investigator subsequently considers treatment related.

Dose-limiting toxicity (DLT) is defined in protocol section 5.1.1 and collected in eCRF.

Adverse event incidence tables will be presented by cohort and total, the number (n) and percentage (%) of subjects experiencing an AE. In a subset of tables, also all occurrences will be counted providing a severity of occurrence of the AE. The denominator for computation of percentages is the Safety Population within each cohort.

Not treatment emergent AE(s) summary:

- Listing of (not treatment emergent) AEs showing cohort, subject identifier, SOC, PT, verbatim term, date and day of onset, end date/time, duration, outcome, severity, date of death (if relevant), relationship to study treatment, action taken, AE seriousness and criteria.

TEAE(s) summaries:

The following TEAE summaries will be generated for the Safety Population.

Overview of TEAEs, summarizing number (%) of subjects with any

- (related/all) TEAE
- (related/all) Serious TEAE
- DLT
- (related/all) TEAE leading to death
- (related/all) TEAE of grade 3 or higher
- (related/all) TEAE leading to drug interruption
- (related/all) TEAE of special interest (AESI)
- (related/all) TEAE leading to permanent discontinuation

- TEAEs by primary SOC and PT, showing number (%) of subjects with at least one TEAE, sorted alphabetically by SOC and decreasing incidence of PTs within SOC for the total column. This sorting order will be applied to all other tables, unless otherwise specified.
- TEAEs by PT, sorted by decreasing frequency in the total column.
- All at least possibly drug related TEAEs by primary SOC and PT, showing number (%) of subjects with at least one possibly related TEAE, sorted by sorting order defined above.
- All TEAEs by maximal severity, presented by primary SOC and PT, showing number (%) of subjects with at least one TEAE by severity (ie, mild, moderate, or severe), sorted by sorting order defined above.

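### A pre-dose adverse event with blank causality would be classed by the SAP as a drug-related TEAE, although the protocol says pre-dose events are listed only (minor)

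*SAP*

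**What the plan says.** SAP 2.5.1.2, under the relationship to investigational product, states: "If the assessment of the relationship to investigational product is missing, then the relationship to investigational product has to be assumed as related". It adds that "the AE considered as such in the derived analysis variable", so the imputed value is an analysis value and not only a display convention. No onset condition is attached.

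SAP 2.4.5.1 defines a TEAE by three limbs joined by or. The first covers events that occur after first dosing. The second is: "Is considered treatment-related regardless of the start date of the event, or". The third covers events present before first dosing that worsen, or that the investigator later judges to be related.

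SAP 2.1.4.1 says that AEs "will be captured from the time the informed consent is obtained until the participant terminates participation in the study". Pre-dose events can therefore be in the database. SAP 2.4.5.1 plans an output for events that are not treatment-emergent: "Listing of (not treatment emergent) AEs showing cohort, subject identifier".

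Protocol 10.5 has the same three limbs and then adds: "AEs that occur after informed consent but before first dosing of study medication will not be summarized but will be listed". The SAP does not repeat that sentence. Protocol 10.7 has its own missing-data convention for the summary of drug-related AEs: apart from the two unrelated categories, "all other categories, including missing, will be considered as" drug related.

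**The concern.** Setting a missing causality to related is a usual conservative convention, and it is sensible for events on treatment. The trouble comes from combining it with a TEAE limb that ignores the start date. An event that began before any infusion cannot tell the reader about a dose or an infusion time. Under the two rules, a blank field alone is enough to move it out of the non-treatment-emergent listing and into the TEAE and related-TEAE tables. If it is serious or Grade 3 or higher, it enters those rows as well.

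These tables are presented by cohort, and the cohorts are small. The study is meant to inform the choice of dose and infusion time partly on tolerability, so a single stray record would show.

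**Working it through.** The documents give no figure on this point, so there is none to reproduce. The check applies the rules to each kind of record and then sizes one misclassified subject.

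**Step 1: the rules as written.**
- Related = Possible, Probable or Definite (Protocol 10.7), or missing (SAP 2.5.1.2).
- TEAE = onset after first dose, or related, or worsened after first dose (SAP 2.4.5.1).
- Related TEAE = TEAE and related.

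Possible stands for all three recorded related categories. Post-dose means within the TEAE period. Each cell gives TEAE / related TEAE.

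| Onset | Not Related | Doubtful | Possible | Missing |
|---|---|---|---|---|
| Pre-dose, not worsened | no / no | no / no | yes / yes | **yes / yes** |
| Pre-dose, worsened | yes / no | yes / no | yes / yes | yes / yes |
| Post-dose | yes / no | yes / no | yes / yes | yes / yes |

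The cell in bold is the defect. The same event marked Not Related or Doubtful stays out of the tables. The non-TEAE listing does not protect the blank one, because the second limb has already made it a TEAE.

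**Step 2: the rules with the proposed change.** Missing becomes related only if the event starts or worsens on or after first dose, and the second limb uses recorded causality only. Of the 12 cells, only the bold one changes, to no / no. Missing causality still counts as related in the other two rows.

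**Step 3: size of one record.** SAP 2.4.5.1 takes the Safety Population in each cohort as denominator. A cohort has 8 subjects: 6 on ublituximab and 2 on placebo who cross over after Day 28 (SAP 1.1; Protocol 5.1). For a subject with no other qualifying event in the row:
- cohort of 8, crossovers pooled: 1/8 = 12.5 points;
- the 6 initially on ublituximab: 1/6 = 16.7 points;
- six cohorts of 8: 1/48 = 2.1 points.

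**Step 4: chance of at least one such subject.** The documents give no rate of missing causality. The share q of subjects with a pre-dose, non-worsening, blank-causality record is therefore an assumption, varied over a range. The chance of at least one among n subjects is 1 − (1 − q)^n.

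| Assumed q | n = 8 | n = 48 | Expected among 48 (48q) |
|---|---|---|---|
| 0.5% | 3.9% | 21.4% | 0.24 |
| 1% | 7.7% | 38.3% | 0.48 |
| 2% | 14.9% | 62.1% | 0.96 |
| 5% | 33.7% | 91.5% | 2.4 |

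This shows only how the answer depends on q. It does not predict a count.

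**The case against.** The best case for the plan has four parts.

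**Few such records should exist.** The AE row of the Protocol Section 7 table starts at Week 1 Day 1 and is empty at screening. Protocol 10.7.1 starts general AE recording on Day 1. Before that it asks for events tied to protocol-mandated interventions such as procedures or washout, and Protocol 10.8.2 has SAEs counted from consent. Protocol 10.7 and 10.7.1 require a causality opinion on AEs, and Not Related is available for a pre-dose event. A reader might infer that screening events are the ones most likely to lack a causality entry, or that many are affected. No document says so. This part of the objection stands, and it limits the likely number. It does not empty the cell: SAP 2.1.4.1 captures events from consent, and the SAP plans a listing for events that are not treatment-emergent.

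**The SAP inherited both rules.** Protocol 10.5 has the same second limb, and Protocol 10.7 counts missing as drug related. A reader might infer that the SAP departed from a clean protocol. It did not, because the tension begins in the protocol. What the SAP adds is a missing-causality rule written into the derived variable without the protocol's restriction to one summary. What it drops is the list-only sentence.

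**The second limb may mean only the investigator's recorded judgement.** That reading is coherent. The third limb speaks of what the investigator considers, and nothing in the SAP says that the derived relationship variable feeds the TEAE flag. But the second limb does not name the investigator, and SAP 2.5.1.2 says the imputed event is considered related. A programmer could follow either reading, which is reason enough to settle it.

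**The consequences are limited.** Safety analyses are descriptive. DLTs are confined to the first 4 weeks of treatment, so a pre-dose event cannot become one. Protocol 8.1.1.1 lists infusion-related reaction, pyrexia, chills and headache among related events seen in more than 20% of subjects on single-agent ublituximab. Many subjects would therefore already count in the any-TEAE and related-TEAE rows, and the full 1/8 shift would often not occur there. This stands as well.

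**Conclusion.** The concern holds for one kind of record only: onset before first dose, no worsening, causality missing. For it, the literal SAP rules give a TEAE and a related TEAE, against the protocol's list-only sentence. No SAP text exempts it.

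The documents do not support a wider claim that screening events in general become TEAEs, since those assessed as unrelated and not worsening stay out. Nor do they support any forecast of how many records are affected. The 12.5- or 16.7-point shift assumes that the affected subject has no other event in the same row. Which figure applies depends on whether crossovers are pooled with their cohort.

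The severity is minor. It is still worth correcting because the plan should give one answer, the cohorts are small and the change costs almost nothing.

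**What to change.** Make four short changes to the SAP:

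1. In 2.5.1.2, impute missing causality as related only for AEs whose onset (imputed where the date is partial) or worsening is on or after first dose.
2. In 2.4.5.1, state that imputed causality is never used to decide treatment emergence, so that the second limb rests on recorded causality.
3. Restore the Protocol 10.5 sentence that events before first dosing are listed and not summarized. Word it to apply to events that meet none of the TEAE limbs, so that it does not collide with the second and third.
4. Define first dose as the first ublituximab dose for the ublituximab Safety Population tables, and as the first placebo dose for the Placebo Safety Population tables. The TEAE definition refers only to study medication. Without this, a placebo-period event with blank causality in a crossover subject could still count as a related TEAE in the ublituximab tables.

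The cost is a few sentences and one condition in the AE derivation. No data collection changes, and missing causality still counts as related for every event that starts or worsens on treatment.

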2.5.2 Windows for Time Points

MRIs are linked to specific visits, so it is not necessary to assign visits based on relative timing. Other efficacy assessments will be summarized by the nominal visit as well and no visit window will be defined.

For safety assessments, the reference date for the derivation of relative days of events or findings will be the date of first dose as documented in the eCRF. All available values obtained between 2 visits including unscheduled measurements will be assigned to the appropriate visit window as specified in section 2.5.3. In the event of multiple measurements of the same test in the same window, the one closest to the targeted visit date will be used for the by-visit summary, in case of equal distance the later observation will be selected. For further details please see the section "Unscheduled Visits" as well.

